3.2 Secondary Objective(s) & Hypothesis(es)

In subjects with HCC receiving pembrolizumab plus BSC vs. placebo plus BSC:

- 1) Objective: To compare objective response rate (ORR) per RECIST 1.1 assessed by a blinded central imaging vendor.
Hypothesis: Pembrolizumab increases ORR per RECIST 1.1, assessed by a blinded central imaging vendor.
- 2) Objective: To evaluate the duration of response (DOR), disease control rate (DCR) and time to progression (TTP), per RECIST 1.1 assessed by a blinded central imaging vendor.
- 3) Objective: Evaluate the safety and tolerability profile of pembrolizumab.

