All adverse events that occur after the consent form is signed but before treatment allocation/randomization must be reported by the investigator if they cause the subject to be excluded from the trial, or are the result of a protocol-specified intervention, including but not limited to washout or discontinuation of usual therapy, diet, placebo treatment or a procedure. From the time of treatment allocation/randomization through 30 days following cessation of treatment, all adverse events must be reported by the investigator. Such events will be recorded at each examination on the Adverse Event case report forms/worksheets. The reporting timeframe for adverse events meeting any serious criteria is described in section 7.2.3.1. The investigator will make every attempt to follow all subjects with non-serious adverse events for outcome.

Electronic reporting procedures can be found in the Electronic Data Capture (EDC) data entry guidelines. Paper reporting procedures can be found in the Investigator Trial File Binder (or equivalent).

7.2.1 Definition of an Overdose for This Protocol and Reporting of Overdose to the Sponsor

In this trial, an overdose is any dose higher than ≥ 1000 mg (5 times the protocol defined dose) of pembrolizumab. No specific information is available on the treatment of over dose of pembrolizumab. In the event of overdose, study treatment should be discontinued and the subject should be observed closely for signs of toxicity. Appropriate supportive treatment should be provided if clinically indicated.

If an adverse event(s) is associated with (“results from”) the overdose of Sponsor's product or vaccine, the adverse event(s) is reported as a serious adverse event, even if no other seriousness criteria are met.

If a dose of Sponsor's product or vaccine meeting the protocol definition of overdose is taken without any associated clinical symptoms or abnormal laboratory results, the overdose is reported as a non-serious Event of Clinical Interest (ECI), using the terminology “accidental or intentional overdose without adverse effect.”

All reports of overdose with and without an adverse event must be reported by the investigator within 24 hours to the Sponsor either by electronic media or paper. Electronic reporting procedures can be found in the EDC data entry guidelines. Paper reporting procedures can be found in the Investigator Trial File Binder (or equivalent).

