7.2.3 Immediate Reporting of Adverse Events to the Sponsor

7.2.3.1 Serious Adverse Events

A serious adverse event is any adverse event occurring at any dose or during any use of Sponsor's product that:

- Results in death;
- Is life threatening;
- Results in persistent or significant disability/incapacity;
- Results in or prolongs an existing inpatient hospitalization;
- Is a congenital anomaly/birth defect;
- Is an other important medical event.

Note: In addition to the above criteria, adverse events meeting either of the below criteria, although not serious per ICH definition, are reportable to the Sponsor in the same timeframe as SAEs to meet certain local requirements. Therefore, these events are considered serious by the Sponsor for collection purposes.

- Is a new cancer (that is not a condition of the study);
- Is associated with an overdose.

Refer to [Table 7](#) for additional details regarding each of the above criteria.

For the time period beginning when the consent form is signed until treatment allocation/randomization, any serious adverse event, or follow up to a serious adverse event, including death due to any cause, other than progression of the cancer under study (reference Section 7.2.3.3 for additional details), that occurs to any subject must be reported within 24 hours to the Sponsor if it causes the subject to be excluded from the trial, or is the result of a protocol-specified intervention, including but not limited to washout or discontinuation of usual therapy, diet, placebo treatment or a procedure.

For the time period beginning at treatment allocation/randomization through 90 days following cessation of treatment, or 30 days following cessation of treatment if the subject initiates new anticancer therapy, whichever is earlier, any serious adverse event, or follow up to a serious adverse event, including death due to any cause, other than progression of the cancer under study (reference Section 7.2.3.3 for additional details) whether or not related to the Sponsor's product, must be reported within 24 hours to the Sponsor either by electronic media or paper. Electronic reporting procedures can be found in the EDC data entry

guidelines. Paper reporting procedures can be found in the Investigator Trial File Binder (or equivalent).

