| | Is a new cancer (that is not a condition of the study) (although not serious per ICH definition, is reportable to the Sponsor within 24 hours to meet certain local requirements); or | |
| | Is an overdose (whether accidental or intentional). Any adverse event associated with an overdose is considered a serious adverse event for collection purposes. An overdose that is not associated with an adverse event is considered a non-serious event of clinical interest and must be reported within 24 hours. | |
| | Other important medical events that may not result in death, not be life threatening, or not require hospitalization may be considered a serious adverse event when, based upon appropriate medical judgment, the event may jeopardize the subject and may require medical or surgical intervention to prevent one of the outcomes listed previously (designated above by a †). | |
| Duration | Record the start and stop dates of the adverse event. If less than 1 day, indicate the appropriate length of time and units | |
| Action taken | Did the adverse event cause the Sponsor's product to be discontinued? | |
| Relationship to Sponsor's Product | Did the Sponsor's product cause the adverse event? The determination of the likelihood that the Sponsor's product caused the adverse event will be provided by an investigator who is a qualified physician. The investigator's signed/dated initials on the source document or worksheet that supports the causality noted on the AE form, ensures that a medically qualified assessment of causality was done. This initialed document must be retained for the required regulatory time frame. The criteria below are intended as reference guidelines to assist the investigator in assessing the likelihood of a relationship between the test drug and the adverse event based upon the available information. The following components are to be used to assess the relationship between the Sponsor's product and the AE; the greater the correlation with the components and their respective elements (in number and/or intensity), the more likely the Sponsor's product caused the adverse event (AE): | |
| | Exposure | Is there evidence that the subject was actually exposed to the Sponsor's product such as: reliable history, acceptable compliance assessment (pill count, diary, etc.), expected pharmacologic effect, or measurement of drug/metabolite in bodily specimen? |

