8.6.1.2 Overall Survival

The non-parametric Kaplan-Meier method will be used to estimate the survival curves. The hypotheses of treatment difference in survival will be tested by the stratified log -rank test. A stratified Cox proportional hazard model with Efron's method of tie handling will be used to estimate the magnitude of the treatment difference (i.e., the hazard ratio). The hazard ratio and its 95% confidence interval from the stratified Cox model with a single treatment covariate will be reported. The stratification factors used for randomization will be applied to both the stratified log-rank test and the stratified Cox model. The same 5 strata defined for the PFS analysis (see Section 8.6.1.1) will be used for the OS analysis.

Subjects in the control arm are expected to discontinue treatment earlier compared to subjects in the pembrolizumab arm, and may switch to another anti PD-1 treatment following the verification of progressive disease by blinded central imaging vendor review. Exploratory analyses to adjust for the effect of treatment switching to other PD-1 therapies on OS may be performed based on recognized methods, e.g. the Rank Preserving Structural Failure Time model proposed by Robins and Tsiatis [53], two-stage model, etc., based on an examination of the appropriateness of the data to the assumptions required by the methods.

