8.6.2 Statistical Methods for Safety Analyses

Safety and tolerability will be assessed by clinical review of all relevant parameters including AEs, laboratory tests, vital signs, etc.

Tiered Approach

The analysis of safety results will follow a tiered approach ([Table 12](#)). The tiers differ with respect to the analyses that will be performed. For this protocol, there are no Tier 1 events.

Tier 2 parameters will be assessed via point estimates with 95% confidence intervals provided for between-group comparisons; only point estimates by treatment group are provided for Tier 3 safety parameters.

AEs (specific terms as well as system organ class terms) will be classified as belonging to "Tier 2" or "Tier 3", based on the number of events observed. Membership in Tier 2 requires that at least 4 subjects in any treatment group exhibit the event; all other AEs and predefined limits of change will belong to Tier 3.

The threshold of at least 4 events was chosen because the 95% confidence interval for the between-group difference in percent incidence will always include zero when treatment groups of equal size each have less than 4 events and thus would add little to the interpretation of potentially meaningful differences. Because many 95% confidence intervals may be provided without adjustment for multiplicity, the confidence intervals should be regarded as a helpful descriptive measure to be used in review, not a formal method for assessing the statistical significance of the between-group differences in AEs and predefined limits of change.

Continuous measures such as changes from baseline in laboratory, vital signs, that are not pre-specified as Tier-1 endpoints will be considered Tier 3 safety parameters. Summary statistics for baseline, on-treatment, and change from baseline values will be provided by treatment group in table format.

In addition, the broad clinical and laboratory AE categories consisting of the percentage of subjects with any AE, any drug related AE, any Grade 3-5 AE, any serious AE, any AE which is both drug-related and Grade 3-5, any AE which is both serious and drug-related, dose modification due to AE, and who discontinued due to an AE, and death will be considered Tier 2 endpoints.

The 95% confidence intervals will be provided for between-treatment differences in the percentage of subjects with Tier 2 events; these analyses will be performed using the Miettinen and Nurminen method [49], an unconditional, asymptotic method.

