8.9 Sample Size and Power Calculations

The study will randomize subjects in a 2:1 ratio into pembrolizumab arm and the control arm. Approximately 408 subjects are required to be enrolled in order to test the OS hypothesis at the desired study requirements.

The analysis of the OS endpoint is event driven. The testing of the OS hypothesis is conducted upon accumulating a preset number of events. The study is designed and will be conducted to accumulate approximately 273 OS events.

PFS Analysis: As described in Section 8.7 Interim Analysis, the main PFS analysis will be conducted at the same time as the first OS IA at approximately Month 22 of the study. It is projected that approximately 331 PFS events will be accumulated at this time. With 331 PFS events, the testing of the PFS hypothesis at Type I error $\alpha=0.2\%$ has 94% power to demonstrate that pembrolizumab is superior to the control with respect to PFS if the underlying PFS hazard ratio (pembrolizumab/control) is 0.60.

The power calculation is based on the following assumptions: 1) PFS follows an exponential distribution with a median of 2.5 months in the control arm; 2) An enrollment period of 16 months; 3) a minimum follow-up of approximately 6 months; and 4) A yearly drop-out rate of $\sim 10\%$.

OS Analysis: A total of 273 OS events are required to test the OS hypothesis at Type I error $\alpha=2.3\%$ with $\sim 92\%$ power (see [Table 14](#)) if the underlying OS hazard ratio (pembrolizumab/control) is 0.65. A total of 408 subjects are needed to be enrolled into the study in order to accumulate 273 OS events at approximately Month 35 of the study.

The sample size and power calculation is based on the following assumptions: 1) OS follows a piece-wise exponential distribution with zero hazard during the first month and a median of 10 months in the control arm; 2) An enrollment period of 16 months; 3) a minimum follow-up of 19 months; and 4) A yearly dropout rate of $\sim 2\%$.

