8.12 Extent of Exposure

The extent of exposure will be summarized as duration of treatment in cycles.

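### Section 8.6.2 and Table 12 compare adverse events only as crude percentages, although the collection window follows treatment duration and control is expected to stop earlier; add time-to-first-event summaries

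*Combined protocol and SAP*

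**What the plan says.** Section 8.6.2 assigns adverse events to Tier 2 or Tier 3 and has no Tier 1 events. For Tier 2, "The 95% confidence intervals will be provided for between-treatment differences in the percentage of subjects with Tier 2 events", by the Miettinen and Nurminen method. The broad categories (any, Grade 3-5, serious, their drug-related versions, dose modification, discontinuation, death) are also percentages of subjects. Table 12 adds nothing tied to time. The section calls the intervals descriptive and not a formal test.

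The length of observation is set elsewhere. Under Section 7.2, from randomization "through 30 days following cessation of treatment, all adverse events must be reported by the investigator". Under Section 7.2.3.1, serious events are reported "through 90 days following cessation of treatment, or 30 days following cessation of treatment if the subject initiates new anticancer therapy", whichever comes first.

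Section 8.6.1.2 states: "Subjects in the control arm are expected to discontinue treatment earlier compared to subjects in the pembrolizumab arm".

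Two provisions bear on timing. Section 8.12 says "The extent of exposure will be summarized as duration of treatment in cycles", and Table 7 in Section 7.2.4 instructs the investigator to "Record the start and stop dates of the adverse event". Neither is carried into an analysis of events against time.

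**The concern.** The plan foresees unequal treatment time, ties the collection window to it, and then compares arms on a measure that ignores it. A subject observed for longer has more opportunity to have a first event, so two arms with the same event rate can show different percentages.

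Safety is a stated secondary aim (Section 3.2: "Objective: Evaluate the safety and tolerability profile of pembrolizumab"), and the broad categories are the figures most readers will look at. The distortion grows with any gain in treatment time, so a trial that succeeds on PFS would blur its own tolerability comparison most. What is at stake is the reading of a descriptive difference, not an efficacy claim or an error rate.

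**Working it through.** **Inputs from the documents.** 408 subjects at 2:1, so 272 versus 136. Section 8.9: "PFS follows an exponential distribution with a median of 2.5 months in the control arm", with a PFS hazard ratio of 0.60. Windows of 30 and 90 days (Sections 7.2 and 7.2.3.1).

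**Check of the PFS inputs.** Power for 331 events, hazard ratio 0.60, one-sided 0.2%, 2:1: √(331 × 2/9) × |ln 0.60| − 2.878 = 8.577 × 0.5108 − 2.878 = 1.503, giving 93.4% against the stated 94%.

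**Assumptions not in the documents.** Treatment time is exponential and tracks planned PFS. The event hazard r is constant and equal in both arms, and is varied because the plan gives no value.

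**Observation time.** L(control) = ln 2 / 2.5 = 0.2773 per month; L(pembrolizumab) = 0.60 × 0.2773 = 0.1664. With the 35-treatment cap, mean time on treatment is 3.6 versus 5.9 months, and the mean 30-day window is 4.6 versus 6.9 months.

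**Crude percentage** with window w (1 or 3 months): 1 − L/(L + r) × exp(−r·w). At r = 0.10, w = 1:
- control: 1 − (0.2773/0.3773) × 0.9048 = 33.5%
- pembrolizumab: 1 − (0.1664/0.2664) × 0.9048 = 43.5%

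Applying the cap and exact days gives 43.4% versus 33.4%.

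The last column shows how often the Miettinen-Nurminen 95% interval excludes zero although the hazards are equal.

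| Rate per month | Window | Duration ratio | Pembrolizumab vs control | Excludes zero |
|---|---|---|---|---|
| 1% | 30 days | 0.60 | 6.6% vs 4.4% | 12% |
| 5% | 30 days | 0.60 | 26.9% vs 19.4% | 37.5% |
| 10% | 30 days | 0.60 | 43.5% vs 33.5% | 49% |
| 10% | 30 days | 0.70 | 40.3% vs 33.5% | 26% |
| 10% | 30 days | 0.80 | 37.6% vs 33.5% | about 12.5% |
| 10% | 30 days | 1.0 | 33.5% vs 33.5% | 5% |
| 20% | 30 days | 0.60 | 62.8% vs 52.4% | 52% |
| 100% | 30 days | 0.60 | 94.8% vs 92.0% | 21% |
| 5% | 90 days | 0.60 | 33.8% vs 27.1% | 28% |
| 10%, first 2 months only | 30 days | 0.60 | 17.5% vs 17.1% | 5% |

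If planned deaths also cut the window (control OS median 10 months, OS hazard ratio 0.65), 10% per month gives 38.1% versus 29.5% at 0.60 (41%) and 33.9% versus 29.5% at 0.80 (14%).

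**Does the remedy work?** Duration ratio 0.60, 30-day window, death competing; pembrolizumab versus control at 3 months:
- Constant 10% per month, equal: 25.1% vs 24.8% (interval excludes zero in 5%).
- Equal early-onset hazard: 17.9% vs 17.8% (5%).
- True 1.5-fold early hazard on pembrolizumab: 25.6% vs 17.8% (45%), so a real excess is still visible.

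At 6 months the constant case gives 41.3% versus 39.6% (7%), mostly because fewer pembrolizumab subjects die first. About 13 of 136 control subjects are then still at risk, against about 50 at 3 months.

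**Person-time rates are not a substitute** (no deaths simulated). With equal early-onset hazards they give 3.0 versus 4.4 per 100 person-months, with zero excluded in 27.5% of trials, nearly always favouring pembrolizumab. With a true 1.5-fold early hazard they give 4.6 versus 4.4 (10%), where the crude percentages show 25.0% versus 17.1% (44%).

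**The case against.** The strongest reply is that nothing here is invalid. The crude percentage is a legitimate quantity: the risk of an event over the treatment actually received plus its window. Section 8.6.2 calls the intervals descriptive and rests safety on clinical review. This stands. It makes the change a cheap improvement, not a correction of an error.

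Second, the 10-point gap sits near the peak of the range. That also stands: rare and near-universal events show only 2 to 3 points. The ratio of 0.60 is the hoped-for PFS effect, not a forecast of treatment time. Section 2.1 lets treatment continue past first progression, and Section 5.8.1 lists other reasons for stopping. The direction does not depend on 0.60, because Section 8.6.1.2 expects it.

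Third, exposure is summarized, onset dates are recorded, and Section 8.0 lets changes to non-confirmatory analyses go into the supplemental SAP. These help only in part: Section 8.0 assigns no safety analysis to that document, and nothing described joins events to time at risk.

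Fourth, a single time-to-event rule cannot serve every Tier 2 item. Death cannot compete with itself, dose modification and discontinuation can occur only on treatment, and any-AE items mix the two windows. This is right, and the fix is written item by item.

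Fifth, an early reading time misses late events; Section 5.2.1.2 notes that immune-related events may arise months after the last dose. Hence the full curve is needed as well.

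**Conclusion.** The point holds as a recommended addition. The safety comparison ignores a difference in observation time that the SAP itself expects, and for accruing events the crude difference can overstate the excess on pembrolizumab. The overstatement runs from about 2 points (1% per month) to about 10 points (10-20% per month) at a duration ratio of 0.60 with the 30-day window. At 10% per month it is about 4 points at 0.80, and it is essentially nil for equal durations or early-onset events. These figures assume equal constant hazards and PFS as a proxy for treatment time.

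Three stronger readings are tempting and unsupported:
- That the plan conceals harm. If control stops earlier, as expected, the distortion inflates accruing harm on pembrolizumab.
- That 49% is a false-positive rate. No test or decision rests on these intervals.
- That the Tier 2 cut-off of 4 suppresses a pembrolizumab signal. Its rationale is stated for equal groups and does not carry over to 2:1: 0/272 versus 3/136 gives z = −2.46, which excludes zero. In the other direction, 3/272 versus 0/136 gives only z = 1.23, and an excess on pembrolizumab needs 8 versus 0 (z = 2.02). This is a wording matter about which descriptive intervals are printed.

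**What to change.** In Section 8.6.2 and Table 12, keep the crude percentages and add supplementary cumulative incidence of first event by arm, with numbers at risk:

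- **Items:** any AE, Grade 3-5 AE, serious AE, and their drug-related versions. Death before the event is competing; a fatal AE counts as the event.
- **Follow-up end, one per item:** 30 days after the last dose for any-AE and Grade 3-5 items, counting only events (serious or not) that start within it; the Section 7.2.3.1 window for serious items.
- **Dose modification and discontinuation due to AE:** end follow-up at treatment cessation, with stopping for other reasons as competing.
- **Death:** leave to the OS analysis.
- **Reading time:** pre-specify an early one, for example 3 months, and show the full curve, because later immune-related events fall after it and few control subjects remain at risk by 6 months.
- **Section 8.12:** add person-months at risk by arm. Do not use person-time rates alone.
- **Optional:** delete the equal-size rationale for the Tier 2 cut-off or restate it for 2:1.

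The cost is a few extra tables from onset dates, dosing dates and deaths already collected. A small bias remains if stopping is related to event risk. With a shared gamma frailty of variance 0.5 on event, death and stopping, cumulative incidence is 22.7% versus 21.8% at 3 months and 34.3% versus 31.6% at 6 months, against 38.0% versus 29.3% for the crude percentages.

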4.2.4.4 Safety Endpoints

The safety objective of this trial is to characterize the safety and tolerability of pembrolizumab in subjects with previously systemically treated HCC. The primary safety analysis will be based on subjects who have toxicities as defined by NCI-CTCAE, version 4.0 (see Section 12.6).

The attribution to drug, time-of-onset, duration of the event, its resolution, and any concomitant medications administered will be recorded. AEs will be analyzed including, but not limited to, all AEs, SAEs, fatal AEs, and laboratory changes. Furthermore, specific events will be collected and designated as events of clinical interest (ECIs) as described in Section 7.2.3.2.

The mandatory Safety Follow-Up Visit should be conducted approximately 30 days after the last dose of trial treatment or before the initiation of a new anti-neoplastic treatment, whichever comes first. All AEs that occur prior to the Safety Follow-Up Visit should be recorded. Subjects with an AE of Grade ≥ 1 will be followed until the resolution of the AE to Grade 0-1 or until the beginning of a new anti-neoplastic therapy, whichever occurs first. All SAEs that occur within 90 days following cessation of treatment, or 30 days following cessation of treatment if the subject initiates new anticancer therapy, whichever is earlier, should be followed and recorded.

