4.3 Benefit/Risk

Subjects in clinical trials generally cannot expect to receive direct benefit from treatment during participation, as clinical trials are designed to provide information about the safety and effectiveness of an investigational medicine. However, experience with this drug approved in other indications, as well as with similar drugs in HCC suggests that study subjects may receive a clinical benefit (see Section 4.1.1).

The benefit-risk profile for pembrolizumab in HCC population is unknown since these subjects were not previously studied. The safety and efficacy data generated to date provide a favorable risk-benefit assessment for the continued use of pembrolizumab as a treatment for advanced/metastatic melanoma and NSCLC, and as an investigational medicinal product in subjects with triple negative breast cancer, squamous cell carcinoma of the head and neck, urothelial tract cancer, colorectal cancer, adenocarcinoma of the stomach/gastroesophageal junction, renal cell carcinoma, hematologic malignancies, multiple myeloma, and other advanced solid tumors. Based on pembrolizumab data from other indications and from data in HCC patients from other agents in the class, a favorable benefits-risk profile is anticipated. No unexpected risks have been reported in HCC with other immune check point inhibitors other than transient elevations in alanine aminotransferase (ALT) and aspartate aminotransferase (AST).

Additional details regarding specific benefits and risks for subjects participating in this clinical trial may be found in the accompanying IB and Informed Consent documents.

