Table 12 Analysis Strategy for Safety Parameters

| Safety Tier | Safety Endpoint | 95% CI for Treatment Comparison | Descriptive Statistics |
|-------------|--|---------------------------------|------------------------|
| Tier 2 | Any AE | X | X |
| | Any Serious AE | X | X |
| | Any Grade 3-5 AE | X | X |
| | Any Drug-Related AE | X | X |
| | Any Serious and Drug-Related AE | X | X |
| | Any Grade 3-5 and Drug-Related AE | X | X |
| | Dose Modification due to AE | X | X |
| | Discontinuation due to AE | X | X |
| | Death | | |
| | Specific AEs, SOCs, or PDLCs (incidence ≥ 4 of subjects in one of the treatment groups) | X | X |
| Tier 3 | Specific AEs, SOCs or PDLCs [‡] (incidence < 4 of subjects in all of the treatment groups), AEOSI | | X |
| | Change from Baseline Results (Labs, ECGs, Vital Signs) | | X |

AE = adverse event; AEOSI = adverse events of special interest; ECG = electrocardiogram; PDLC = pre-defined limit of change; SOC = system organ class.

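### Table 12 leaves the grouped AEOSI category without a between-arm interval, omits hepatic ECIs from every tier, and makes the tier of a frequent AEOSI term ambiguous

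*Combined protocol and SAP*

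**What the plan says.** Section 8.6.2 sorts safety parameters into tiers. The rule begins "AEs (specific terms as well as system organ class terms) will be classified as belonging to" Tier 2 or Tier 3, according to how many events are seen: "Membership in Tier 2 requires that at least 4 subjects in any treatment group exhibit the event". Tier 2 parameters get a Miettinen-Nurminen 95% interval for the difference between arms, while "only point estimates by treatment group are provided for Tier 3 safety parameters". Nine broad categories, such as any serious AE, any Grade 3-5 AE and discontinuation due to an AE, are named as Tier 2 in the text whatever their count.

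Table 12 repeats the incidence rule. Its Tier 2 row covers specific AEs, SOCs and PDLCs reaching 4 "of subjects in one of the treatment groups". Its Tier 3 row covers the same items below 4 and then adds one more entry: "of subjects in all of the treatment groups), AEOSI". The incidence condition is in the parentheses; AEOSI stand outside them.

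Section 8.4.2 takes the safety endpoints from Sections 4.2.4.4 and 7.2. Section 4.2.4.4 says that "specific events will be collected and designated as events of clinical interest (ECIs"), and Section 7.2.3.2 defines the hepatic ECIs by ALT, AST, bilirubin and clinical decompensation criteria, with 24-hour reporting. ECIs are not mentioned in Section 8.6.2 or Table 12. AEOSI are expanded as an abbreviation under Table 12, but no event list is given or referenced there, and their relation to ECIs is not stated.

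**The concern.** Tier placement decides whether the arms are compared with an interval. Two things go wrong.

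First, a programmer cannot tell from Table 12 what to do with an AEOSI term seen in, say, 10 subjects. It meets the Tier 2 incidence condition and is also named in the Tier 3 row. Followed literally, the Tier 3 entry drops the interval.

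Second, neither grouped category, any AEOSI or any hepatic ECI, has a planned between-arm comparison. Section 4.3 states: "The benefit-risk profile for pembrolizumab in HCC population is unknown since these subjects were not previously studied". It also singles out transient ALT and AST elevations as the signal seen with other agents in the class. Section 5.2.1.3 notes that HCC patients have many non-drug causes of abnormal liver tests. In that setting a count in the pembrolizumab arm says little without the placebo arm, and the size and precision of the difference is the useful summary.

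**Working it through.** **1. Text and table side by side.**

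| Item | Text of 8.6.2 | Table 12 | Interval planned? |
|---|---|---|---|
| Specific AE term or SOC, at least 4 subjects in an arm | Tier 2 | Tier 2 | Yes |
| Nine broad AE categories | Tier 2 | Tier 2 | Yes, per the text |
| AEOSI term, at least 4 subjects in an arm | Tier 2 as a specific term | Fits Tier 2 and Tier 3 | Unclear |
| Any AEOSI (group) | Not addressed | Tier 3 | No |
| Any hepatic ECI (group) | Not addressed | No row | No |

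For single AEOSI terms there is a conflict between rows. For the groups there is a gap: the text is silent and the table supplies either a Tier 3 entry or nothing.

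**2. The plan's own figure.** The threshold of 4 is justified because the interval "will always include zero when treatment groups of equal size each have less than 4 events". The Miettinen-Nurminen limits are the values d at which

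z(d) = (p1 - p2 - d) / sqrt{[r1(1 - r1)/n1 + r2(1 - r2)/n2] x N/(N - 1)} = ±1.96,

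where p1 and p2 are the observed rates, r1 and r2 are the maximum-likelihood rates under r1 - r2 = d, and N = n1 + n2. With 204 per arm:

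- 3 vs 0: z(0) = 1.74; interval -0.40 to 4.24 points, which includes zero.
- 4 vs 0: z(0) = 2.01; interval 0.09 to 4.94 points, which excludes zero.

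The stated basis reproduces for equal arms. (Allocation here is 2:1, where it does not carry over exactly; that is a separate matter.)

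**3. Would single terms do the group's work?** Inputs: 408 subjects at 2:1, so 408 x 2/3 = 272 and 408 x 1/3 = 136. The only related rate in the documents is about 1% for immune-related hepatitis (Section 5.2.1.3). The chance that a term with rate p reaches 4 of 272 is

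P(X ≥ 4) = 1 - sum over k = 0 to 3 of C(272, k) p^k (1 - p)^(272 - k).

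This gives 0.29 at 1%, 0.79 at 2%, 0.96 at 3% and 0.999 at 5%. Common hepatic terms will almost surely get an interval. A 1% immune-related term usually will not on its pembrolizumab-arm count. For example, five AEOSI terms seen in 2 different pembrolizumab subjects each and in no placebo subject would all be Tier 3 terms. Grouped, they make 5 x 2 = 10 vs 0, with an interval of 0.9 to 6.6 points. The plan provides no such row.

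**4. What a group-level row would show.** The documents give no composite AEOSI or hepatic ECI rate, so all counts below are assumed.

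| Counts (of 272 vs 136) | Rates | Difference, points | 95% CI, points |
|---|---|---|---|
| 14 vs 7 | 5.1% vs 5.1% | 0.0 | -5.5 to 4.3 |
| 27 vs 7 | 9.9% vs 5.1% | 4.8 | -1.1 to 9.8 |
| 41 vs 14 | 15.1% vs 10.3% | 4.8 | -2.5 to 11.1 |
| 49 vs 11 | 18.0% vs 8.1% | 9.9 | 2.9 to 16.2 |
| 54 vs 14 | 19.9% vs 10.3% | 9.6 | 2.0 to 16.3 |

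Some of these intervals exclude zero and some do not. Under Table 12 none would be planned at group level.

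**The case against.** A reader might infer that the key safety events of this trial get no between-arm interval at all. The documents do not support that. Ascites, encephalopathy, variceal bleeding, or a raised ALT, AST or bilirubin reported as an AE each get an interval once 4 subjects in an arm have the term. The serious, Grade 3-5, drug-related, dose-modification and discontinuation categories get one in any case.

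A reader might also infer that Table 12 contradicts the Tier 2 rule outright. For the groups it does not, because the rule is written for specific terms and organ classes. Only the single AEOSI term at 4 or more subjects falls under two entries.

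Three further points stand. The plan calls these intervals descriptive and unadjusted, so no decision rule depends on them. Arm-level counts remain available, so an interval could be worked out later, and safety also has clinical and eDMC review. And a group-level interval would not cleanly isolate the drug effect: Section 8.6.1.2 expects control subjects to stop treatment earlier, AE reporting is tied to treatment cessation (Section 7.2), and hepatic ECIs count even when attributed to progression (Section 7.2.3.2).

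What does not stand is that term-level intervals make the group unnecessary. Rare terms often fall below 4, and the broad categories mix them with everything else. Laboratory-defined hepatic ECIs might enter as PDLCs, but the plan does not say what the PDLCs are, so this cannot be relied on.

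**Conclusion.** The point holds at group level. Table 12 puts AEOSI in Tier 3 without an incidence condition, which leaves the tier of a frequent AEOSI term ambiguous and gives the grouped category no between-arm interval. Hepatic ECIs are prespecified and collected but appear in no tier. The consequence is a missing descriptive comparison for the categories in which rare immune-related and hepatic terms would be pooled. Type I error, power and data collection are untouched.

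How much information is lost depends on event rates that the documents do not give. Over the assumed counts shown, the missing interval ranges from one centred near zero to one lying wholly above it. The arm sizes of 272 and 136 assume that all 408 subjects are randomized 2:1 and treated. The change is worth making because it settles a stated analysis choice at very little cost.

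**What to change.** In Section 8.6.2 and Table 12:

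- State that AEOSI terms with at least 4 subjects in any treatment group follow the Tier 2 rule, and keep only AEOSI terms below 4 in Tier 3.
- Add three rows to the Tier 2 broad categories: any AEOSI, Grade 3-5 AEOSI, and any hepatic ECI as defined in Section 7.2.3.2, each with the Miettinen-Nurminen 95% interval already specified.
- Reference the AEOSI term list and state how AEOSI relate to ECIs, so that the new rows have a defined content.

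The cost is a table and text edit, a reference to a fixed term list, and a few programmed rows from data already collected. Trial conduct does not change. The only downside is a few more unadjusted intervals, which the existing statement in Section 8.6.2 on descriptive use already covers.
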